## **10.6 Secondary objective 5**

### **To evaluate the overall survival and survival rate at 24 and 36 weeks.**

Overall survival (OS), defined as the time from the date of inclusion until the date of death due to any cause, will be calculated using Kaplan-Meier (KM) estimates. The KM graph will show the median OS time and the 95% CI will indicate the number of events and patients censored. All patients who discontinue from the study will be followed for survival for 24, 36 and 40 weeks, unless they withdraw their consent, die or are lost-to follow-up, in which case will be censored at the last contact/follow-up.

The survival rate will also be evaluated by the percentage of patients still alive at 24, 36 and 40 weeks.

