6.1.2 Treatment duration

The duration of treatment with eltrombopag will be based on the reasons described below and other reasons for early withdrawal ([Section 7.2.3.17.2.3.1](#)):

- If no partial or complete hematological response is observed at 16 weeks and maintained afterwards, the patient will be withdrawn from the study.
- In patients achieving complete response without transfusion support for a minimum of 8 weeks, the dose of eltrombopag may be reduced by 50%, and discontinued if counts remain stable after 8 weeks at the reduced dose. If relapse occurs after eltrombopag discontinuation, eltrombopag can be reintroduced at the last effective dosage.
- If new clonal cytogenetic abnormalities associated with dysplastic bone marrow findings are observed such as monosomy 7, eltrombopag should be permanently discontinued.

- If the patient develops myelodysplastic syndrome (MDS) or acute myeloid leukemia (AML) assessed by sensitive methods, eltrombopag will be permanently discontinued.
- If other non-clonal and/or cytogenetic abnormalities with uncertain meaning not previously observed and not associated with worsening blood counts or bone marrow dysplastic, the decision of discontinuing eltrombopag is up to the investigator, based on a more frequent bone marrow aspirate monitoring of cytogenetic abnormalities and dysplastic findings.
- If relapse of previous hematological disease occurs, eltrombopag will be permanently discontinued.
- If patient receives a new HSCT, eltrombopag will be permanently discontinued

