7.2.4 Follow-up for survival

All patients who discontinue from the study, regardless the reason of discontinuation, will be followed for survival for 24 and 36 weeks, unless they withdraw their consent, die or are lost-to follow-up, in which case will be censored at the last contact/follow-up.

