10.5.1 Other efficacy objective(s)

- To determine the response in each haematological lineage separately, the absolute frequency and valid percentage of patients who have a response in the neutrophil, platelet, and Hb lineages separately after 16, 24 and 36 weeks of eltrombopag, will be presented with the 95% CI. Descriptive statistics will also be provided between baseline and weeks 16, 24 and 36 for ANC, platelets and hemoglobin levels, and the appropriate paired exploratory tests will be done according to the type of distribution (parametric or not) to assess the statistical significance of the changes.
- To evaluate the overall hematological response rate (partial and complete) at 24 and 36 weeks after the initiation of eltrombopag, the frequency and percentage distribution and the corresponding 95% CI will be provided. This CI will be constructed as for the primary efficacy endpoint. Descriptive statistics will also be provided between baseline and week 24 and week 36 for ANC, platelets count and hemoglobin levels, and the appropriate paired exploratory tests will be done according to the type of distribution (parametric or not) to assess the statistical significance of the changes.
- To evaluate transfusion independence, the percentage of patients who were previously transfusion-dependent and do no longer require a RBC or platelet transfusion before and after the first 16 weeks of treatment will be calculated along with the 95% CI. This CI will be constructed as for the primary efficacy endpoint. The period where patients did not receive any platelet or RBC transfusions during the treatment period and follow-up will also be analyzed.

- To evaluate the discontinuation or reduction of concomitant G-CSF and/or EPO therapy, the percentage of patients who discontinue or reduce by $\geq 50\%$ from baseline the use of concomitant G-CSF and/or EPO therapy will be calculated along with the 95% CI. This CI will be constructed as for the primary efficacy endpoint.
- Overall survival, defined as the duration from inclusion in the study to date of death (whatever the cause), will be estimated with the Kaplan-Meier curves method and two-sided 95% CI for the estimated median. All patients who discontinue from the study, regardless the reason of discontinuation, will be followed for survival for 24 and 36 weeks, unless they withdraw their consent, die or are lost-to follow-up, in which case will be censored at the last contact.

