## 7 END OF STUDY FORM

The categorical variable to be described is:

- Did the patient complete the study? (No / Yes). In negative case, it will be shown a multiple response table with the following options:
  - Adverse event(s). In this case, specify the adverse event.

- Pregnancy.
- Abnormal laboratory value(s).
- Abnormal test procedure result(s).
- Unsatisfactory therapeutic effect.
- Study terminated by sponsor.
- Non compliance with study treatment.
- Protocol deviation.
- Physician decision.
- Subject withdrew consent.
- Lost to follow-up.
- Administrative reasons.
- Death.
- Study indication.
- Other. In case of other, specify.

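### The overall survival censoring clause lists death as a reason for censoring. This contradicts the endpoint's definition and, if applied as written, would overstate Kaplan-Meier survival.

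*SAP*

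**What the plan says.** SAP 10.6 gives the endpoint: "Overall survival (OS), defined as the time from the date of inclusion until the date of death due to any cause". It is estimated by Kaplan-Meier, and the output "will indicate the number of events and patients censored". The same paragraph adds a rule for everyone who leaves the study, with survival checked at weeks 24, 36 and 40. Under that rule, follow-up goes on "unless they withdraw their consent, die or are lost-to follow-up, in which case will be censored at the last contact/follow-up".

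Protocol 10.5.1 has the same rule for weeks 24 and 36: "unless they withdraw their consent, die or are lost-to follow-up, in which case will be censored at the last contact". The clause also stands in the protocol summary (study design), Table 3-1, 4.1, 7.2.4 and 7.3.1.3, and in SAP 2.2. With 10.5.1 and SAP 10.6 that makes eight places.

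No other OS censoring rule exists. Protocol 10.4.3 mentions censoring in its title but gives no rule, and SAP section 3 names only the Kaplan-Meier method. Nothing states that a death after discontinuation is an event on its date, or when a patient who completes the study alive is censored.

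Who discontinues is set partly by Protocol 6.1.2: "If no partial or complete hematological response is observed at 16 weeks and maintained afterwards, the patient will be withdrawn from the study". Relapse of the underlying disease and a new transplant permanently stop eltrombopag under the same section, and Protocol 7.2.3.1 makes the 6.1.2 reasons withdrawal criteria.

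**The concern.** Death is the only event in this analysis, yet the clause puts it beside consent withdrawal and loss to follow-up and sends all three to censoring at last contact. For example, a patient withdrawn at week 16 for non-response who dies at week 22 would be an event under the definition and a censored observation under the clause. Both instructions stand in one SAP paragraph.

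If the clause is programmed as written, real deaths leave the only time-to-event analysis in the plan. The error runs one way, towards better survival. The counts of events and censored patients would be wrong too, and a single-arm trial has no control curve that might expose the problem.

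**Working it through.** **The plan's own figure.** No expected survival, event count or power is stated for OS. The only design calculation is the one-sided 95% Clopper-Pearson lower limit for the primary endpoint (Protocol 10.7). With n = 33 and x = 0.45 × 33 = 14.85, the 5th percentile of Beta(14.85, 19.15) is 30.08%, against 30.1% stated. It reproduces and does not depend on the OS rule.

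**Inputs.** n = 33 and 45% response (Protocol 10.7); withdrawal of non-responders (Protocol 6.1.2); two-year OS of 34.6% in a cited early-PGF series (Protocol 1.1). Assumptions, not in the documents: constant hazard, two years taken as 104 weeks, and the share q of deaths that fall under the clause.

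**Step 1: patients exposed.** Non-responders at week 16: 33 × (1 − 0.45) = 18.15, about 18. Other discontinuations add to this.

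**Step 2: deaths by week 36.** S(36) = S(104)^(36/104).
- Two-year survival 34.6%: 0.346^(36/104) = 0.693, so 33 × 0.307 = about 10.1 deaths.
- Two-year survival 60% (assumed): 0.838, about 5.3 deaths.
- Two-year survival 80% (assumed): 0.926, about 2.5 deaths.

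**Step 3: Kaplan-Meier under the literal clause.** Survival times for 33 patients were simulated from an exponential distribution (1,000 runs), with a random share q of deaths recoded as censored at the time of death. Mean KM estimate at week 36:

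| True 36-week survival | q = 0 | 25% | 50% | 75% | 100% |
|---|---|---|---|---|---|
| 69% | 68.8% | 75.4% | 83.1% | 90.9% | 100% |
| 80% | 80.1% | 84.2% | 89.4% | 94.5% | 100% |
| 90% | 90.1% | 92.5% | 94.9% | 97.4% | 100% |

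In the 69% row the mean number of counted events falls from 10.3 to 7.8, 5.1, 2.6 and 0. As a check, recoding a random share q leaves a hazard of (1 − q) times the original, so KM should be near S^(1−q): 0.69^0.75 = 0.757, 0.69^0.50 = 0.831, 0.69^0.25 = 0.911. These agree with the simulation.

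**Step 4: what q might be.** Take 15 responders with hazard h and 18 non-responders with hazard HR × h, with h chosen so that overall 36-week survival is 0.693. Deaths among non-responders between weeks 16 and 36 number 18 × [exp(−16·HR·h) − exp(−36·HR·h)]. For HR = 1, 2 and 4 (assumed) this gives 2.8, 3.4 and 3.9 of 10.1 deaths, or 28%, 34% and 38%. Week-16 non-responders alone therefore put q between the 25% and 50% columns. Other discontinuers would raise it by an amount the documents do not let one estimate.

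**Step 5: the median.** With 69% to 93% alive at week 36 in the Step 2 scenarios, and follow-up ending at week 36 or 40, median OS would probably not be reached under either coding.

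**The case against.** The strongest reply is that the sentence is mainly a follow-up rule. Survival follow-up naturally ends when a patient withdraws consent, dies or is lost, and Protocol 4.1 and SAP 2.2 close the sentence by saying that study visits then stop. The endpoint definition in the same SAP paragraph is explicit, and the SAP asks for a number of events, which can only be deaths. A careful programmer would code deaths correctly. This stands as a reason not to say that deaths will be lost. It does not remove the contradiction, because no passage says which instruction prevails.

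Deaths are also visible elsewhere: the percentage alive is reported separately, survival status is collected at visits (Protocol 7.2.2.4 and 7.2.2.5), and deaths go on a Death form (Protocol 8.1.1). A miscoded curve would conflict with these. That also stands, and it limits the damage to the KM output.

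The 34.6% figure comes from early PGF. This trial also takes secondary PGF, requires Karnofsky of at least 90%, and excludes active GVHD, active malignancy and disease progression, so its patients may do better. The 80% and 90% rows are there for that reason.

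A reader might infer three stronger things. First, that most deaths fall after discontinuation: the documents give no split, and Step 4 does not give a majority from week-16 non-responders alone. Second, that the curve will show no events and 100% survival: that is the extreme column, where every death falls under the clause. Third, that on-study deaths are censored too, because death is among the non-completion reasons in SAP section 7 ("Did the patient complete the study? (No / Yes). In negative case, it will be shown a multiple response table with the following options"). The documents do not say that a death on study counts as discontinuing for this clause, and that reading would leave an OS analysis with no events at all.

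**Conclusion.** The contradiction is real and appears in both documents: death is the OS event, and it is also a stated reason for censoring after discontinuation. If the clause is followed, KM survival is biased upward and the event and censoring counts are wrong. The size depends on assumptions the documents do not settle, namely the true survival and the share of deaths after discontinuation. At 69% true 36-week survival, a share of 25% to 50% would lift the estimate by about 6 to 14 percentage points (to 75% and 83%). At 80% the same shares would lift it by about 4 to 9 points (to 84% and 89%).

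OS is a descriptive secondary endpoint with no hypothesis (Protocol 10.4.2) and no power statement (Protocol 10.8). The primary analysis, the sample size and the percentage alive at weeks 24 and 36 are not affected. It should be corrected, but it does not threaten the trial's main conclusion.

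**What to change.** Remove death from the censoring clause in all eight places: the protocol summary, Table 3-1, 4.1, 7.2.4, 7.3.1.3 and 10.5.1, and SAP 2.2 and 10.6. Death may stay as a reason why follow-up ends. Add in SAP 10.6 and Protocol 10.5.1:

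*Death from any cause, whether during the study or after discontinuation, is an event on the date of death. Patients not known to have died (consent withdrawn, lost to follow-up, or alive at the end of follow-up, including completers) are censored at the date last known alive.*

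This also supplies the missing censoring date for completers. The same edit can align the follow-up horizon, which is weeks 24, 36 and 40 in SAP 10.6 but weeks 24 and 36 in the protocol.

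The cost is a short wording change repeated in eight places. The protocol part needs a written amendment under Protocol 12.1. No new assessments and no change in sample size are needed, since survival status and deaths are already collected. It is worth confirming that the forms hold the date of death and the date last known alive for patients who have left the study.

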- The overall survival rate will be evaluated by the percentage of patients still alive at 24 and 36 weeks.

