10.7 Sample size calculation

The primary objective is to evaluate the efficacy of eltrombopag on overall hematopoietic response (partial or complete) by 16 weeks in patients with PGF after receiving an allo-HSCT. When the sample size is 33 patients and the proportion of responses with eltrombopag is assumed to be 45% in this sample, a one-sided 95% CI of such proportion will have a length of 0.149 towards its lower end. In other words, this CI will provide enough evidence that the actual proportion of responses in the target population is above 30%, because its lower limit (as per the sampling distribution) would be 30.1.

Table 10-1 Sample size justification

Confidence level	Minimally acceptable response	Distance of observed response to lower limit	Observed proportion	Actual lower limit	Sample size
95%	>30%	14.9%	45%	30.1%	33

The calculation of the sample size has been performed using the exact method described by Clopper and Pearson (*Newcombe RG. Two-sided confidence intervals for the single proportion: comparison of seven methods. Stat Med 1998; 17:857-72*) as implemented in the version 15 of the PASS software (NCSS statistical software: PASS version 15, available at: ncss.com/software/pass).

Statistical Methodology:

As mentioned, a one-sided confidence interval will be constructed for the proportion of responders using the formula indicated on [Section 10.4.2](#).

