- Follow-up for Survival: all patients who discontinue from the study, regardless the reason of discontinuation, will be followed for survival for 24 and 36 weeks, unless they withdraw their consent, die or are lost-to follow-up, in which case will be censored at the last contact/follow-up, and study visits will no longer be carried out.

At 36 weeks of the study, the suitability of continuing with eltrombopag will be evaluated by the investigator, and the supply of the drug will be only commercial. Novartis will not supply eltrombopag after the end of the study.

The number of patients planned to be enrolled for the study is 33.

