### **3 STATISTICAL METHODS**

Quantitative variables are described with measures of central tendency and dispersion: mean, median, SD, Q1, Q3, minimum and maximum).

Qualitative variables are described using absolute and relative frequencies (N, %). Two percentage columns are presented, total percentage (total %) and valid percentage (valid %), that is, the percentage over the sum of valid responses plus missing values and the percentage over the total of valid responses. When there are not missing values both of them are equal, and then only one will be show.

[figure not shown]
In the analysis of contingency tables as well as for the comparison of proportions and / or frequency distributions, the chi-square test (or Fisher's exact when appropriate) will be used.

For dependent samples, parametric (t-test paired) or non-parametric (Wilcoxon) statistical tests will be performed depending on the distribution of the sample.

The "time to event" variables (overall survival) will be analyzed using the Kaplan-Meier method.

These tests will be used in all bilateral cases and with a level of significance of 0.05. In cases where a p-value less than 0.05 appears, it refers to the existence of statistical significance.

Data will be analyzed using SPSS v22.0.

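### The survival rate at weeks 24 and 36 is planned only as a crude percentage with no rule for unknown status, and SAP 10.6 adds a week 40 that other sections contradict

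*SAP*

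**What the plan says.** **Survival rate.** Protocol 10.5.1 states: "The overall survival rate will be evaluated by the percentage of patients still alive at 24 and 36 weeks". Table 3-1 and section 7.3.1.3 define it the same way. SAP 10.6 adds a third time point: "The survival rate will also be evaluated by the percentage of patients still alive at 24, 36 and 40 weeks".

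**Overall survival.** SAP 10.6 says that this "will be calculated using Kaplan-Meier (KM) estimates", with censoring at last contact. The planned summaries are the median with a 95% confidence interval and the numbers of events and censored patients. Protocol 10.5.1 likewise plans the curve and a two-sided interval for the median. Neither document names a Kaplan-Meier estimate at a fixed week.

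**Missing categorical data.** SAP section 3 prints two columns, a total % and a valid %: "the percentage over the sum of valid responses plus missing values and the percentage over the total of valid responses".

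**Follow-up of discontinued patients.** Protocol 7.2.4 says that they "will be followed for survival for 24 and 36 weeks, unless they withdraw their consent, die or are lost-to follow-up". Protocol 4.1, 7.3.1.3 and 10.5.1 and SAP 2.2 give the same two time points. SAP 10.6 says that they are followed for 24, 36 and 40 weeks.

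**The concern.** The plan expects some patients to have unknown survival status and has a rule for them on the Kaplan-Meier curve. It has none for the survival rate reported beside it. Two columns of the same table could then give different rates, and neither need agree with the curve.

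The fixed-week rate may carry the survival message. If the curve does not fall to 50% within the roughly 40 weeks of the study, the median is not reached, and the rate is the only planned number a reader can use.

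Week 40 adds a separate problem. Patients without a response at week 16 are withdrawn (protocol 6.1.2). Whether their status at week 40 will be known depends on which follow-up statement applies, and the statements disagree.

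**Working it through.** **Inputs from the documents.** Sample size: "The number of patients planned to be enrolled for the study is 33" (SAP 2.2). Assumed response: "When the sample size is 33 patients and the proportion of responses with eltrombopag is assumed to be 45% in this sample" (protocol 10.7). So 0.45 × 33 = 14.85, about 15 responders and 18 non-responders.

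**Inputs assumed.** The documents give no expected deaths or losses. I take 0 to 6 deaths and 1 to 5 patients of unknown status at week 36.

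**The plan's own figure.** No survival figure is stated. The only design figure is that "a one-sided 95% CI of such proportion will have a length of 0.149 towards its lower end". The protocol's formula with n = 33, x = 14.85 and one-sided α = 0.05 gives a lower limit of 30.08% and a distance of 0.1492, so it reproduces. It is used here only as the source of the 33 and the 45%.

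**Weeks 24 and 36.** Let D be known deaths, U unknown and A = 33 − D − U known alive.

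- Total % = A/33. Read as the survival rate, this has the effect of counting unknowns as not alive. Each unknown patient moves it by 1/33 = 3.0 points.
- Valid % = A/(33 − U), which drops unknowns altogether.
- Upper bound = (A + U)/33, with all unknowns alive.

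With unknowns censored before the week in question, the Kaplan-Meier estimate lies between the valid % and the upper bound. The valid % equals Kaplan-Meier with those patients removed from the start. Keeping them at risk until they are censored can only raise each factor of the product.

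| D | U | Total % | Valid % | Upper bound |
|---|---|---|---|---|
| 0 | 1 | 97.0 | 100.0 | 100.0 |
| 3 | 3 | 81.8 | 90.0 | 90.9 |
| 3 | 5 | 75.8 | 89.3 | 90.9 |
| 6 | 5 | 66.7 | 78.6 | 81.8 |

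**Worked illustration at week 36.** Assume deaths at weeks 4, 8, 12, 18, 24 and 30, and censoring at weeks 6, 14, 17 and 20.

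- Kaplan-Meier: 32/33 × 30/31 × 29/30 × 26/27 × 24/25 × 23/24 = 0.804.
- Total %: 23/33 = 69.7%.
- Valid %: 23/29 = 79.3%.

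The valid % is 1.1 points below Kaplan-Meier and the total % is 10.7 points below.

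**Week 40, if withdrawn patients are followed only to week 36.** Footnote * of Table 7-1 places the Week 40 assessments of prematurely withdrawn patients 30 days after the last dose. After a week-16 withdrawal that is about study week 20, so this visit cannot supply week-40 status. Take 18 patients withdrawn at week 16, all deaths before week 36, no other losses, and surviving withdrawn patients censored at week 36.

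| Deaths (in withdrawn) | Total % | Valid % | Kaplan-Meier |
|---|---|---|---|
| 0 (0) | 15/33 = 45.5 | 15/15 = 100 | 100 |
| 3 (2) | 14/33 = 42.4 | 14/17 = 82.4 | 30/33 = 90.9 |
| 6 (4) | 13/33 = 39.4 | 13/19 = 68.4 | 27/33 = 81.8 |

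Here the valid % understates survival whenever a withdrawn patient has died: those deaths stay in the count while the surviving withdrawn patients drop out. With no deaths and 10 to 24 responders still on study, the total % runs from 30.3% to 72.7% while the valid % stays at 100%.

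**Week 40, if SAP 10.6 governs.** Status is unknown only after consent withdrawal or loss to follow-up, so the position is like that at week 36.

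**Which governs.** The objective heading of SAP 10.6 names weeks 24 and 36 only, as do SAP 2.1 and 2.2 and the protocol sections above. The survival-status row of Table 7-1 has three marks, whose spacing would fit weeks 24, 36 and 40. The table layout is broken in the text available, so it cannot settle the question.

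**The case against.** Kaplan-Meier with censoring is already planned in the same SAP section, and the crude rate is additional to it. A reader can take week-24 and week-36 survival from the curve. SAP section 3 prints both percentages whenever values are missing, so the ambiguity would be visible. It does not say that unknown means dead, and protocol 10.4.3 says missing data will be shown as missing. Because discontinued patients are followed for survival, few should be unknown at weeks 24 and 36. The endpoint is one of several descriptive secondary endpoints in a single-arm study without formal hypotheses.

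Most of this stands, and it keeps the point small. It does not settle which percentage is the survival rate, and it does not supply a fixed-week estimate that handles censoring, with its interval.

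A reader might infer that withdrawn patients are simply not followed to week 40, so that the week-40 rate must describe mostly responders. The documents do not support that. The sentence in SAP 10.6 just before the week-40 rate says discontinued patients are followed to week 40. What can be shown is a contradiction, and the large week-40 gaps above hold only if the protocol's follow-up governs.

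A reader might also conclude that the crude percentage should be removed. It is a protocol-defined secondary endpoint (Table 3-1, 7.3.1.3, 10.5.1), so removing it in the SAP alone would depart from the protocol.

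**Conclusion.** The point holds in a limited form. The survival rate is a crude percentage with no stated denominator for unknown status, in a plan that expects censoring and takes only the median from the Kaplan-Meier curve.

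At weeks 24 and 36 the effect is modest. Over the assumed range of 0 to 6 deaths and 1 to 5 unknown, the valid % is at most 3.2 points below the upper bound (81.8 − 78.6), and so no further than that from Kaplan-Meier. The total % falls 3.0 points below that bound for each unknown patient, up to 15.2 points with five (5/33).

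At week 40 the documents contradict each other. The effect is large under the protocol's follow-up (for example 42.4% or 82.4% against 90.9%) and similar to week 36 under SAP 10.6. These sizes rest on assumed deaths and losses, and the week-40 figures also on the 45% response assumption. The primary analysis and the sample size are not affected.

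**What to change.** In SAP 10.6:

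1. Report Kaplan-Meier estimates of survival at weeks 24 and 36, with two-sided 95% confidence intervals from the planned curve, as the main survival rate.
2. Keep the protocol's crude percentage alive as a descriptive figure. State its denominator and show the numbers alive, dead and of unknown status at each week.
3. Reconcile the follow-up statements in SAP 10.6, SAP 2.2 and the protocol. Drop the week-40 rate unless survival contact at calendar week 40 is confirmed for withdrawn patients. If it is confirmed, report a Kaplan-Meier estimate there too.

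The cost is a minor SAP edit and one more reported estimate at each time point. Items 1 and 2 need no new data. Keeping week 40 would mean bringing the protocol's follow-up text into line, because the SAP alone cannot create that contact.
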